7.3.1. COVID-19 diagnosis

The definitions used for COVID-19 diagnosis will depend on the data source, for example, the primary care data sources usually do not contain the laboratory values. All the analyses will be run on the main definition while the alternative definitions will be used for secondary objective 4 - to explore how COVID-19 is captured across different databases. (see Appendix 1 for code lists)

1. Catch-all (main definition, the most sensitive)

¹ Cardiovascular disease as a subgroup variable has a different definition from the composite cardiovascular event as an adverse event which is focused on acute and severe outcomes.

Defined either as the first confirmed diagnosis for COVID-19 **OR** the first SARS-CoV-2 positive PCR test, if both present the earliest date will be considered.

Alternative definitions

2. Diagnosis confirmed (diagCOVID-19)

Defined as one of the following medical codes for COVID-19 at any time (first occurrence considered):

- U07.1 COVID-19, virus identified
- U07.2 COVID-19, virus not identified

3. Laboratory confirmed (labCOVID-19)

Defined as a record of SARS-CoV-2 positive PCR as performed on nasopharyngeal swabs and/or on respiratory tract secretions and aspirates.

We will not include the testing for the presence of antibodies due to the issue of not knowing the point of infection via antibody testing. If patient has more than one test, first occurrence will be considered

4. Symptomatic COVID-19.

At least two symptoms of the following

- Cough
- Dyspnoea
- Fever, unspecified
- Malaise and fatigue
- Myalgia
- Anosmia, Hyposmia or Dysgeusia episodes

5. Suspected COVID-19

- Coronavirus as the cause of diseases classified to other chapters
- Coronavirus infection, unspecified site
- Other viral pneumonia
- Acute bronchitis due to other specified organisms
- Unspecified acute lower respiratory infection
- Bronchitis, not specified as acute or chronic
- Adult respiratory distress syndrome
- Other specified respiratory disorders
- Special screening examination for other viral diseases
- Contact with and exposure to other communicable diseases

This classification is aligned with the ICD-10 International coding guidance on COVID-19 disease (20)

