7.7.6 Explore the performance of different COVID-19 coding definitions (secondary objective 4)

The PheValuator is a tool that can be used to estimate the performance of rule-based coding definitions when validation by clinical adjudication of patient records is not possible. (29) This tool will be used to evaluate different COVID-19 definitions as described in section 7.3.1. The method involves three steps:

- (1) Developing a probabilistic diagnostic predictive model for a rule-based case definition:
- (2) Determine the probability for everyone in a large group of subjects to be a case.
- (3) Evaluating the performance characteristics of the rule-based case definition.

This process can be repeated for each case definition constructed.

To construct the diagnosis predictive model, a very specific outcome cohort is needed (where cases have a high certainty to be true positives) which for this study will be the laboratory confirmed SARS-CoV-2 PCR test cases (cCOVID-19). This outcome cohort is nested in the target cohort which contains all subjects positive and a random selection of all subjects negative from the study population, to be used for the model.

This specific outcome cohort will be used to discriminate between positive and negative cases and to both ‘train’ and test the diagnostic prediction model. The PatientLevelPrediction R package (<https://github.com/OHDSI/PatientLevelPrediction>) will be used to create this model and all available data (except the code used to create the true positives) of a 75% random sample of each target cohort will be used.

Once the model is developed, internally validated on the remaining 25% of each target cohort dataset, calibrated and achieves good performance characteristics, this model will be applied to a larger study cohort (called the evaluation cohort, which is also sampled randomly from the study population), where each subject will have a predicted probability calculated for the case definition of interest. The probability of the case definition determined by the model is then used as the probabilistic gold standard with which to examine the following the performance characteristics of each case definition:

- (1) Sensitivity defined as True Positives/ (True Positives + False Negatives)
- (2) Specificity defined as True Negatives / (True Negatives + False Positives)
- (3) Positive Predictive Value defined as True Positives/ (True Positives + False Positives)

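### Objective 4 scores the PCR definition with a model trained on PCR positives but blind to the PCR code, so the PPV and sensitivity of labCOVID-19 cannot be read as accuracy and the catch-all is affected too

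*Protocol*

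**What the plan says.** Section 7.7.6 announces that "This tool will be used to evaluate different COVID-19 definitions as described in section 7.3.1". Those definitions include labCOVID-19, "Defined as a record of SARS-CoV-2 positive PCR as performed on nasopharyngeal swabs" or on other respiratory samples; diagCOVID-19, which is U07.1 or "U07.2 COVID-19, virus not identified"; and the catch-all, which is the earlier of the two.

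The model needs a very specific outcome cohort, one "where cases have a high certainty to be true positives", and 7.7.6 chooses PCR-confirmed cases. It labels them cCOVID-19 rather than labCOVID-19, but both labels denote a positive PCR record. For the predictors, "all available data (except the code used to create the true positives) of a 75% random sample of each target cohort will be used". After validation on the remaining 25%, "The probability of the case definition determined by the model is then used as the probabilistic gold standard", and sensitivity, specificity, PPV and NPV are computed against it for each definition. No definition is exempted.

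Negatives and the evaluation cohort are both drawn from the study population, which 7.1 describes as diagCOVID-19 or labCOVID-19 patients. Section 7.9.1 states that PCR results are available only in SIDIAP.

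**The concern.** Withholding the PCR code while the model is built is sensible, since otherwise the model would only read back its own label. The difficulty arises when the same model is used to grade that label. A PCR-positive patient with few other records receives a low probability and counts largely as a false positive, although the plan chose PCR positives because they are almost certainly cases.

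The treatment is also uneven. Only the code behind the true positives is removed, so U07.1 and U07.2, the symptom codes and the suspected-disease codes all remain predictors. Among the single-criterion definitions, labCOVID-19 is the only one whose own code the model cannot see.

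At stake is how objective 4 is read. The catch-all is the main definition for every analysis, and 7.7.6 promises insight into broader against narrower definitions. A PPV well below 1 for labCOVID-19 or the catch-all would look like evidence against PCR or against the main cohort, when it may only reflect the withheld code.

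**Working it through.** The protocol gives no expected value for objective 4, so there is no figure to reproduce.

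**Identity.** With a probabilistic standard, the PPV of a definition is the mean model probability p among those who meet it. For a calibrated model, the PPV of labCOVID-19 is E[p × PCR]/P(PCR) = E[p²]/E[p]. Its sensitivity is E[p × PCR]/E[p], which is the same quantity. It is below 1 unless the other records identify PCR status perfectly.

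**Simplest case.** Let the diagnosis code be the only informative predictor. Write s = P(code | PCR positive), q = P(PCR positive | code), π = PCR-positive prevalence and r = P(PCR positive | no code). Then:

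- PPV(diagCOVID-19) = q
- PPV(labCOVID-19) = s·q + (1 − s)·r
- PPV(catch-all) = [s + (1 − s)·r] / [s/q + 1 − s]
- If PCR positives are accepted as cases, PPV(labCOVID-19) is about 1 and PPV(catch-all) is at least its PCR-positive share, 1/[s/q + 1 − s].

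In a general population r = π(1 − s)/(1 − πs/q). If the population holds only diagCOVID-19 or labCOVID-19 patients, anyone without a code is PCR positive, so r = 1.

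**Inputs.** None of s, q or π is in the protocol. The assumed ranges are s 0.3 to 0.9, q 0.3 to 0.9 and π 1% to 5%.

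**One cell in full** (π = 0.01, s = 0.5, q = 0.6, general population): r = 0.005/(1 − 0.00833) = 0.00504. PPV(labCOVID-19) = 0.30 + 0.5 × 0.00504 = 0.30. PPV(catch-all) = 0.5025/1.3333 = 0.38, against a PCR-positive share of 1/1.3333 = 0.75. With r = 1, PPV(labCOVID-19) = 0.30 + 0.50 = 0.80.

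| Population | s | q | diagCOVID-19 | labCOVID-19 | Catch-all | PCR-positive share of catch-all |
|---|---|---|---|---|---|---|
| General, π = 1% | 0.5 | 0.6 | 0.60 | 0.30 | 0.38 | 0.75 |
| General, π = 1% | 0.9 | 0.3 | 0.30 | 0.27 | 0.29 | 0.32 |
| General, π = 1% | 0.9 | 0.9 | 0.90 | 0.81 | 0.82 | 0.91 |
| Code or PCR only | 0.5 | 0.6 | 0.60 | 0.80 | 0.75 | 0.75 |
| Code or PCR only | 0.9 | 0.9 | 0.90 | 0.91 | 0.91 | 0.91 |

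In the general population, labCOVID-19 scored below diagCOVID-19 in all 24 cells run, with PPV 0.10 to 0.81 for labCOVID-19 and 0.18 to 0.82 for the catch-all. In the restricted population the order reversed in all 12 cells.

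**Variants.**

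- U07.1 and U07.2 as separate predictors (π = 2%): either order, for example diagCOVID-19 0.48 against labCOVID-19 0.73, or 0.57 against 0.51.
- Test-performed concept (Appendix 1, 1.3) left in as a predictor: either order, for example 0.60 against 0.46, or 0.30 against 0.51.
- Simulated logistic model with several predictors and a 75/25 split: labCOVID-19 below diagCOVID-19 at q = 0.6 and 0.9 (for example 0.60 against 0.43), and about equal or above at q = 0.3 (for example 0.30 against 0.36).

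The PPV of labCOVID-19 was below 1 in every scenario, from 0.10 to 0.97.

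**The case against.** **The ranking is not established.** A reader might infer that objective 4 is bound to report a low PPV for labCOVID-19 and to place it below the diagnosis codes. The protocol does not support that. It gives no overlap of codes with PCR, and on the 7.1 meaning of study population the order reverses. This part of the objection stands. That reading is no rescue, however. The reversal arises because the absence of a diagnosis code then reveals the label, and the catch-all covers everyone, so its sensitivity is 1 and its specificity 0 whatever the data.

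**The model must first perform well.** Section 7.7.6 applies it only once it is calibrated and performing well, and a low PPV for labCOVID-19 means that PCR status is poorly predicted. But no threshold is given, and good discrimination does not prevent the problem. In the general-population cell with π = 0.01, s = 0.9, q = 0.3, the false-code rate is (0.03 − 0.009)/0.99 = 0.021, so the AUC is (0.9 + 0.979)/2 = 0.94, while PPV(labCOVID-19) is 0.27.

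**The 5 by 5 matrix already shows overlap.** It gives model-free overlap with labCOVID-19, which helps. It is not restricted to tested persons, and it does not stop the model-based values from being reported.

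**The consequences are limited.** This is correct. Objective 4 is exploratory, the main definition is already fixed, and labCOVID-19 can be scored only in SIDIAP.

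**Conclusion.** The point holds for objective 4. As 7.7.6 is written, the model-based PPV and sensitivity of labCOVID-19 do not measure its accuracy, and they fall below what the plan's premise of near-certain true positives implies. In a general population the catch-all is pulled below its own PCR-positive share through its PCR-only members. The comparison with diagCOVID-19 is not even-handed, and labCOVID-19 may rank below it.

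That the value is below 1 follows from the text, given a calibrated model and other records that do not predict PCR perfectly. The size (0.10 to 0.97) and the direction of the ranking rest on assumed overlap and on which population supplies the negatives and the evaluation cohort. The protocol gives no overlap, and its stated population makes the comparison uninformative. The other objectives do not depend on these results.

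**What to change.** In 7.7.6:

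1. Name labCOVID-19 as the reference and report no model-based PPV or sensitivity for it.
2. Report the catch-all's model-based values only with a statement that its PCR-positive members are scored without their PCR code. Do not set the probability to 1 for PCR positives while keeping the unrevised model probability for everyone else, because that probability was fitted with the positives included. With the code as sole predictor and q = 0.60, this would give diagCOVID-19 a PPV of 0.60 + 0.40 × 0.60 = 0.84 even if no remaining coded patient were a case (truth 0.60).
3. In SIDIAP, cross-tabulate diagCOVID-19 and the symptomatic and suspected definitions directly against PCR result among tested persons. Appendix 1 already lists positive and negative result concepts.
4. Draw negatives and the evaluation cohort from a population not restricted to diagCOVID-19 or labCOVID-19 patients, and say so.

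The cost is one fewer model-based row, some extra tabulation and a few lines of text. The tested-only table describes a selected group and should be labelled as such.

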7.7.7 Meta-analysis

All the proposed analyses will be conducted for each database separately, with cumulative HR estimates (at 30 days follow-up) for each treatment group of interest combined using the DerSimonian-Lard random effects meta-analysis methods when $I^2 \leq 40\%$. The standard errors associated with the cumulative HRs will be used to weight individual database estimates using the inverse variance weighting methods. No meta-analysis will be conducted when I^2 for a given drug-outcome pair is $>40\%$.

7.7.8 Sensitivity analysis

For objective 2 and 3, with regards to the reference group for incidence rates

As a sensitivity analysis, the reference group for incidence rates will be replaced with ‘other immunotherapies’ (see Appendix 3 for details).

For prevalent users’ cohorts, the definition of remote users:

A sensitivity analysis to exclude those patients for whom short term duration of corticosteroid use (14 days) is identified prior to COVID-19 diagnosis.

For objectives 2 and 3, if the number of patients censored due to switching is higher than 70%, a sensitivity analysis will be performed, namely an intention to treat approach (ITT), such that after initial exposure is defined to allocate patients to one of the four treatment groups, the denominator is then person-time observed (irrespective of treatment status), rather than person-time treated.

7.8 Quality Control

IQVIA Quality Management System (QMS)

At the study level, all aspects of the study from protocol development to the reporting of the results are conducted within the work-frame of IQVIA Quality Management System (QMS) and in accordance to the following policies and procedures:

RWI_OP_PM0020 “Record Management Guideline”

RWI_OP_PM0005 “Quality Control Strategy” policy

RWI_OP_BIOS0003 “Statistical Analysis Plan for Non-Interventional Retrospective Studies”

RWI_OP_PM0004 “Quality Control of Project Deliverables”

According to the policies and procedures above, a Quality Control plan for the study will be developed and executed, which will include quality control on study methodology, statistical analysis plan, programming, data management and analysis, study results, conclusions and study report.

Furthermore:

The study Quality Control plan will establish ownership for the execution of the individual Quality Control steps. The principle of the independence of Quality Control applies

The Principal-in-Charge of the study will ensure that individuals responsible for the execution of specific Quality Control steps will have knowledge, capability and experience which are adequate for the task.

The result of the execution of the individual steps of the Quality Control plan will be documented, and include the required corrective actions, if any.

The execution of any required corrective action will be documented.

The executed Quality Control plan will be subjected to a final review and approval for sufficiency and completeness from the Principal-in-Charge of the study

Also, the Principal-in-Charge of the study will verify training compliance of IQVIA employees contributing to the study, as per IQVIA procedure RWI_WI_PM0035 “Real-World Project Specific Training and Staff Transition.

7.9 Limitations of the Research Methods

7.9.1 Study design limitation

COVID-19 diagnosis misclassification – the diagnosis of COVID-19 in absence of confirmatory test has a high likelihood to be misclassified as the disease symptoms are unspecific. This misclassification is more likely for patients treated in primary care, e.g., those with milder symptoms. In addition, with regards to the availability of results of PCR test for SARS-CoV-2, this is currently available in only one database (SIDIAP).

- **Mitigation:** Different definitions will be explored and compared as part of objective 4. We will base the main definition on definite diagnosis not on symptoms only and supplement with confirmatory tests when available

Confounding by indication and severity may occur when the different treatments are prescribed depending upon the physician's assessment of the patient's health status in relation to the outcome of interest. The risk of this confounding is high due to glucocorticoids being indicated in severe COVID-19 cases only and therefore correlated with the increase in severity.

- **Mitigation:** No comparative analysis will be performed. This confounding needs to be considered when interpreting the incidence rates obtained.

Selection bias occurs when there is a selective recruitment into the study of subjects that are not representative of the population intended to be studied, so that the association between exposure and outcome of interest is different in the included and excluded population.

- **Mitigation:** Minimal exclusion criteria will be used. In addition, we have included data sources with large or whole national coverage and both ambulatory and hospital setting.

Exposure to glucocorticoids in hospital setting might be underrepresented as glucocorticoid might be captured only as ward stock and not as individual dispensation.

On-treatment exposure classification was considered suitable for this study in order to facilitate comparison with clinical trials results. However, this way of classifying exposure does not consider subsequent treatments and might miss a deterioration of disease.

The **short duration of follow-up** will allow only the capture of acute adverse events.

Prescribing patterns of corticosteroids over time

Due to the short study period (1 year) any time series analysis cannot be undertaken, and the observed trends cannot be confirmed.

If exposure to glucocorticoids as second or third treatment occurs very often, a large proportion of patients will be censored, leading to limited data to assess the outcomes of interest.

Mitigation – an ITT sensitivity analysis is proposed in case censoring is very large (>70%)

7.9.2 **Databases related limitations**

Linkage between primary and secondary care

Seven out of eight databases will not have linkage between primary and secondary setting, and a consequence of this is that patient follow up time will be fragmented. Especially in the hospital setting, the access to medical history of the patient is limited and the patients who had prior exposure of glucocorticoids in primary care risk to be misclassified as naïve users.

Primary care databases

Severe outcomes that lead to hospitalization are less likely to be captured., although hospitalization is captured in some of the primary care databases.

If patients are free to change general practitioners and they are not tracked across different GPs or if they are treated. In private practice, their exposure will be underestimated and the follow up will be fragmented.

As the hospital and ambulatory settings are not linked, patients who had prior exposure of glucocorticoids in hospitals will be misclassified as naïve users.

Hospital setting databases

As the lookback period in the hospital setting is in general absent or reduced, there will be an under-ascertainment of baseline comorbidities.

Mortality data

The mortality information (vital status) is under-captured in some data sources. Three of them, DA Germany, LPD France and LPD Italy do not record vital status at all. For SIDIAP, the vital status comes from a regional mortality register while for HM Hospitales, the vital status comes directly from hospital records. For IMRD UK and IPCI, the vitals status information comes from GP recording.

Section 8.0 Protection of Human Subjects

For this study, participants from various EU member states will process personal data from individuals which is collected in national/regional electronic health record databases. Due to the sensitive nature of this personal medical data, it is important to be fully aware of ethical and regulatory aspects and to strive to take all reasonable measures to ensure compliance with ethical and regulatory issues on privacy.

All the databases used in this study are already used for pharmaco-epidemiological research and have a well-developed mechanism to ensure that European and local regulations dealing with ethical use of the data and adequate privacy control are adhered to.

In agreement with these regulations, rather than combining person level data and performing only a central analysis, local analyses will be run, which generate non-identifiable aggregate summary results. The output files will not contain any data that allow identification of subjects included in the study. IQVIA has an internal set of rules and processes associated with Data quality assurance. Patient confidentiality will be protected according to the EU General Data Protection Regulation (GDPR)] on the protection of individuals. Security of the data will be maintained at all times. Access will be limited to authorized individuals.

Section 9.0 Management and Reporting of Adverse Events/ Adverse Reactions

Pursuant to the EMA requirements for reporting of adverse events for secondary data (GVP module VI, VI.C.1.2.1.2), adverse event reporting will not be conducted as part of this study given the study objectives will be met through the use of secondary data.

Section 10.0 Plans for Disseminating and Communicating Study Results

The final study report will be written in accordance with the GVP guidelines module VIII, (EMA/813938/2011). In accordance with the 2010 EU pharmacovigilance legislation (Articles 10 or 10a of Regulation (EC) No 726/2004; Articles 21a or 22a of Directive 2001/83/EC), information about this PASS will be entered into the publicly available EU PAS register before the start of data collection. Updates to the study protocol in case of substantial amendments, progress reports where applicable, and the final study report will also be entered in the register.

The R script used for this analysis will be published to <https://github.com/OHDSI/> (Observational Health Data Science and Informatics).

Section 11.0 References

Appendix 1 Example of code lists

This appendix provides an overview of the standard concepts and cohort set descriptions that are used to define each indication or risk group. The concept ID refers to the unique ID in the OMOP Common Data Model.

1. Covid-19 diagnosis

1.1. Covid-19 diagnosis

Concept ID	Concept name
37311061	Disease caused by 2019-nCoV
4100065	Disease due to Coronaviridae
439676	Coronavirus infection
37311060	Suspected disease caused by 2019-nCoV

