7.2.2 Patient Selection

7.2.2.1 Inclusion Criteria

Four cohorts will be created based on healthcare setting and type of steroid use. Their eligibility criteria being described below (using Covid-19 catch-all definition Section 7.3.1):

Ambulatory prevalent user

- Have at least 365 days of continuous observation time prior to cohort entry
- Have a glucocorticoid (oral or parenteral) exposure in the 120 days prior to diagnosis date (unrelated to COVID-19 diagnosis)
- Have a positive PCR test for SARS-CoV-2 (labCOVID-19) or a confirmed COVID-19 diagnosis (diagCOVID-19)
- Have no hospitalizations in the 30 days prior to or on index

Ambulatory naive user

- Have at least 365 days of continuous observation time prior to cohort entry
- Have no glucocorticoid (oral or parenteral) exposure in the 120 days prior to index (unrelated to COVID-19 diagnosis)
- Have a positive PCR test for SARS-CoV-2 (labCOVID-19) or a confirmed COVID-19 diagnosis (diagCOVID-19)
- Have no hospitalizations in the 30 days prior to or on index

Hospitalized prevalent user

- Have a glucocorticoid (oral or parenteral) exposure in the 120 days prior to index (unrelated to COVID-19 diagnosis)
- Have a positive PCR test for SARS-CoV-2 (labCOVID-19) or a confirmed COVID-19 diagnosis (diagCOVID-19) (index date)
- Are hospitalized 30 days prior or after diagnosis index date
- Have no intensive services in the 30 days prior to or on index

Hospitalized naïve user

- Have no prior exposures to glucocorticoids in the 120 days prior to index
- Have a positive PCR test for SARS-CoV-2 (labCOVID-19) or a confirmed COVID-19 diagnosis (diagCOVID-19)
- Are hospitalized 30 days prior or after diagnosis index date
- Have no intensive services in the 30 days prior to or on index

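### The only COVID-19 diagnosis concept list mixes suspected and generic coronavirus concepts with the specific one, against the confirmed-diagnosis entry rule in Section 7.3.1

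*Protocol*

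**What the plan says.** Section 7.2.2.1 builds the four cohorts "using Covid-19 catch-all definition Section 7.3.1". That definition reads "Defined either as the first confirmed diagnosis for COVID-19", or the first positive PCR, with the earlier date taken if both exist. Section 7.3.1 runs all analyses on it.

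The diagnosis-confirmed definition (no. 2) names two codes, U07.1 and "U07.2 COVID-19, virus not identified". Suspected COVID-19 is a separate alternative (no. 5), kept for secondary objective 4, and it lists "Coronavirus infection, unspecified site". Section 7.9.1 answers the risk of case misclassification with this statement: "We will base the main definition on definite diagnosis not on symptoms only".

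Appendix 1 holds one COVID-19 diagnosis list, 1.1, with four concepts: disease caused by the 2019 virus (37311061), disease due to the coronavirus family (4100065), coronavirus infection (439676), and "Suspected disease caused by 2019-nCoV" (37311060). No other list is offered for definition 5.

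**The concern.** The body text and the list it points to describe different populations. The body text requires a confirmed case; the list admits a suspected case and infection with any coronavirus.

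Case status carries much of the weight in this design. Section 7.3.2.1 says that indication is not captured, and it treats any of five glucocorticoids started by a naive user from 2 days before to 30 days after the diagnosis date as COVID-19 treatment. Section 7.2.4 names asthma and COPD as conditions for which glucocorticoids are indicated. A patient coded as suspected who in fact had another respiratory illness, and was given a steroid for it, would be counted as a treated COVID-19 patient. That would affect the primary objective (share treated, drug, dose, timing) and the populations behind objectives 2 and 3, and would make databases differ by coding habit. In objective 4, the main and suspected definitions would share concepts, which blurs the 5 by 5 comparison in Section 7.7.6.

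**Working it through.** No sample size or other stated figure depends on this point, so the check sets the texts side by side.

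**1. The chain from eligibility to codes.** Section 7.2.2.1 refers to the catch-all definition in 7.3.1. Section 7.3.1 refers to Appendix 1 for code lists, and the introduction to Appendix 1 says its concepts are those used to define each indication. The only diagnosis list is 1.1.

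**2. Each concept in list 1.1 against Section 7.3.1.**

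| Concept | Specific to COVID-19 and not merely suspected? | Place of such a record in 7.3.1 |
|---|---|---|
| 37311061, disease from the 2019 virus | Yes | Definitions 1 and 2 |
| 37311060, suspected disease from the 2019 virus | No, suspected | Definition 5, by its title |
| 439676, coronavirus infection | No, generic | Definition 5, which lists the unspecified-site code |
| 4100065, disease due to the virus family | No, generic | Not named; definition 5 is the nearest |

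Count: 3 of 4 concepts go beyond the main definition.

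**3. Any rule that removes such patients.** The only exclusion in Section 7.2.2.2 is missing age or sex. List 1.3 holds a negative-test concept, but no eligibility rule uses it.

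**4. Where it would act.** Section 7.9.1 says PCR results are currently available only in SIDIAP, so in 8 - 1 = 7 databases entry rests on diagnosis concepts alone. In SIDIAP the earlier of the two dates counts, so a suspected record could still add a patient or bring the index date forward.

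Seven of eight counts databases, not patients. Section 7.5 gives 153,759 patients in total and 1,417 to 124,221 per database, without naming which is which:
- If SIDIAP is the largest, the other seven hold 153,759 - 124,221 = 29,538 patients (29,538 / 153,759 = 19.2%).
- If SIDIAP is the smallest, they hold 153,759 - 1,417 = 152,342 (99.1%).

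These are patients in databases without a PCR route, not patients wrongly included. No counts per concept are given.

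**5. What misclassification would do to the share treated.** Let m be the share of the cohort without COVID-19, p the steroid use in true cases, and r the ratio of use in the others to use in true cases. Observed use = (1 - m)p + m·r·p = p[1 + m(r - 1)].

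With purely assumed values p = 3% and r = 4 (use of 12% in the others):
- m = 10%: 0.90 × 3% + 0.10 × 12% = 3.9%, a relative excess of 30%.
- m = 20%: 0.80 × 3% + 0.20 × 12% = 4.8%, a relative excess of 60%.

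With r = 1 the excess is zero whatever m is. Over r = 1 to 4 and m = 10% to 20%, the excess runs from 0 to 60%. None of these inputs comes from the protocol.

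**The case against.** A reader might infer that suspected and non-COVID patients will certainly enter every analysis. The protocol does not support that. Appendix 1 is titled as an example and calls itself an overview. List 1.1 is not assigned to any one definition, and since definition 5 has no list of its own, 1.1 may pool the concepts for several definitions. Section 7.3 promises pre-specified concept sets reviewed by a core team, and final sets may sit in documents not shown. Section 7.3.1 itself states the rule for the confirmed definition, U07.1 or U07.2, and nothing says that the appendix overrides it. The laboratory-confirmed definition in objective 4 has its own list (1.2) and is untouched. All of this stands and limits the point to a conflict that must be reconciled.

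A reader might also hold that including U07.2 is an error. It is an openly stated choice within a definition labelled the most sensitive, and Section 7.9.1 admits that diagnosis without a test is prone to misclassification. Calling such cases confirmed is loose wording, but the inclusion is declared.

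Objective 4 will estimate sensitivity, specificity and predictive values for each definition, which is a partial answer. It does not repair the main results: they are run on the main definition only, and the objective 4 model is trained on PCR-positive cases, which Section 7.9.1 says one database can supply.

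The study is descriptive and reports each database separately. That limits the harm to comparative inference but does not help a descriptive estimate whose population is unclear. For prevalent users, Section 7.3.2.1 also asks for a different glucocorticoid or a change in dose or schedule, so the route described above concerns mainly naive users.

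**Conclusion.** The conflict is real and nothing in the protocol resolves it. Entry is described as confirmed or definite, yet three of the four concepts in the only diagnosis list are suspected or generic. Whether such patients enter depends on whether list 1.1 is applied as written, which the protocol leaves open. If it is, the effect falls chiefly on the seven databases without PCR results.

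The number of patients affected and the size of any bias cannot be computed from the documents. The 0 to 60% range shows only how the result depends on assumed inputs. A fixed overstatement of 30% to 60% might be read from it, but that would hold only under the assumed fourfold difference in steroid use. The point should be settled before data extraction, because it decides who belongs to every cohort.

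**What to change.** - Give a separate, labelled concept set for each of the five definitions in Section 7.3.1.
- Move 37311060, 439676 and 4100065 out of the main set to definition 5. First check in each database which concept carries U07.1 and U07.2 records. The protocol gives no mapping, and if U07.2 records sit under the suspected concept, removing it would drop cases that the catch-all definition is meant to include.
- Keep U07.2 in the catch-all as stated, but show the primary results with and without patients who enter only through U07.2 or a suspected or generic concept.

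The cost is a code-list edit before extraction, a mapping check per database and one extra set of tables. The main cohort may become somewhat smaller, with some loss of true cases recorded only under a broad concept; the with-and-without tables keep those patients visible.
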